1.3 Benefit/risk and ethical assessment

Not applicable.

1.4 Study Design

This is a prospective, single-arm, multicenter, phase-IV trial investigating the safety of osimertinib in Indian adult patients with metastatic EGFR-T790M mutation-positive NSCLC. Investigator will be trained on the locally approved prescribing information before the enrolment of the first patient at their site to ensure compliant and proper dosing of the study drug. Patients will be monitored throughout the study period for AEs of osimertinib.

2. Study Objectives

Primary Objective:	Primary Outcome Measure:
To assess the safety of osimertinib among T790M positive NSCLC patients of India	• Number, frequency and proportion of patients with adverse events (AEs), serious adverse events (SAEs) and AEs of special interest (AESI) including interstitial lung disease/pneumonitis-like events, and on-study deaths.

3. Patient Selection, Enrolment, Randomisation, Restrictions, Discontinuation and Withdrawal

Each patient should meet all of the inclusion criteria and none of the exclusion criteria for this study. Under no circumstances can there be exceptions to this rule.

3.1 Inclusion criteria

Each potential patient must satisfy all of the following criteria to be enrolled in the study.

- Patient of either sex and ≥ 18 years of age
- Patients with metastatic EGFR T790M mutation-positive NSCLC, as detected by an appropriate test, who have progressed on or after EGFR TKI therapy by an independent clinical judgment of treating physician based on locally approved prescribing information
- Each patient (or their legally acceptable representative) must sign an informed consent form (ICF) indicating that he or she understands the purpose of and procedures required for the study and are willing to participate in the study. Patients must be willing and able to adhere to the prohibitions and restrictions specified in this protocol, as referenced in the informed consent form (ICF).

3.2 Exclusion criteria

Patients should not enter the study if any of the following exclusion criteria are fulfilled:

- Patient with either the history of hypersensitivity to excipients of the study drug or to drugs with a similar chemical structure or class to the study drug.
- 2 Pregnant and/or lactating women
- Patients participating in any current or future interventional trial will not be enrolled in the current study

Procedures for withdrawal of incorrectly enrolled patients see section 3.4.

3.3 Patient enrolment and randomization

- Approximately 70 patients meeting all inclusion and none of the exclusion criteria will be screened for the study to enroll 60 patients in the current study.
- Patients will be in open label treatment.
- Patients who discontinue the study will not be replaced.
- The E-code is the only patient identification number to be used in CSRs and high level documents.
- Investigator(s) should keep a record, the patient screening log, of patients who entered pre-study screening.
- The Investigator(s) will:
 - Obtain signed informed consent from the potential patient before any study specific procedures are performed.
 - o Assign potential patient a unique enrolment number code.
 - o Determine patient eligibility.
 - o Enroll only eligible patients. If a patient withdraws from participation in the study, then his/her enrolment code cannot be reused.

3.4 Procedures for handling incorrectly enrolled or patients

Patients who fail to meet the eligibility criteria should not, under any circumstances, be enrolled or receive study medication. There can be no exceptions to this rule. Patients who are enrolled, but subsequently found not to meet all the eligibility criteria must not be initiated on treatment, and must be withdrawn from the study.

Where a patient does not meet all the eligibility criteria but is enrolled in error, or incorrectly started on treatment, the Investigator should inform the AstraZeneca study physician immediately, and a discussion should occur between the AstraZeneca study physician and the investigator regarding whether to continue or discontinue the patient from treatment. The AstraZeneca study physician must ensure all decisions are appropriately documented

3.5 Methods for assigning treatment groups

Not applicable- This is a single arm study.

3.6 Methods for ensuring blinding

Not applicable – This is an open-label study.

3.7 Methods for unblinding

Not applicable – This is an open label study.

3.8 Restrictions

The following restrictions apply while the patient is receiving study treatment and for the specified times before and after:

- Females of child-bearing potential should use reliable methods of contraception from the time of screening until 6 weeks after discontinuing study treatment. Acceptable contraception methods are: Total sexual abstinence (abstinence must be for the total duration of the trial and the follow-up period); vasectomised sexual partner plus male condom (with participant assurance that partner received post-vasectomy confirmation of azoospermia); tubal occlusion plus male condom; intrauterine device (IUD) provided coils are copper-banded, plus male condom; intrauterine system (IUS) levonorgestrel intra-uterine system, plus male condom; medroxyprogesterone injections plus male condom; etonogestrel implants plus male condom; normal and low dose combined oral contraceptive pills, plus male condom; intravaginal device (eg ethinylestradiol transdermal system plus male condom; intravaginal device (eg ethinylestradiol and etonogestrel) plus male condom; desogestrel plus male condom.
- Male patients should be asked to use barrier contraceptives (i.e., by use of condoms) during sex with all partners during the trial and for a washout period of 4 months. Male patients should avoid procreation for 4 months after completion of trial treatment. Patients should refrain from donating sperm from the start of dosing until 4 months after discontinuing study treatment.
- Once enrolled all patients must try to avoid concomitant use of medications, herbal supplements and/or ingestion of foods that are known to be potent inducers of CYP3A4 whenever feasible, but patients may receive any medication that is

clinically indicated for treatment of adverse events. Such drugs must have been discontinued for an appropriate period before they enter screening and for a period of 3 months after the last dose of TAGRISSO. All concomitant medications should be captured on the eCRF.

If medically feasible, patients taking regular medication, with the exception of potent inducers of CYP3A4 (see above), should be maintained on it throughout the study period. Patients taking concomitant medications whose disposition is dependent upon BCRP and which have a narrow therapeutic index should be closely monitored for signs of changed tolerability as a result of increased exposure of the concomitant medication whilst receiving TAGRISSO.

Patients taking rosuvastatin should have creatine phosphokinase levels monitored (due to BCRP-mediated increase in exposure). If the patient experiences any potentially relevant AEs suggestive of muscle toxicity including unexplained muscle pain, tenderness, or weakness, particularly if accompanied by malaise or fever, rosuvastatin must be stopped and any appropriate further management should be taken.

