3.9.1 Procedures for discontinuation of a patient from study drug

At any time, patients are free to discontinue study drug or withdraw from the study (i.e., study drug and assessments), without prejudice to further treatment. A patient that decides to discontinue study drug will always be asked about the reason(s) and the presence of any adverse events. If possible, they will be seen and assessed by an Investigator(s). Adverse events will be followed up (See Section 6) and all study drugs should be returned by the patient.

Enrolled patients who discontinue the study prematurely should immediately stop taking study drug and complete the procedures described for End of Treatment Visit, as soon as possible but not later than 7 days after discontinuation of study drug.

If a patient is withdrawn from study, see Section 3.9, 3.10, 3.11.

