Patient participation will include a Screening/Enrolment Phase, a Treatment Phase, and a Follow-up Phase. The Screening Phase will be up to 7 days prior to Cycle 1, Day 1. The Treatment Phase will extend from Cycle 1, Day 1 to Cycle 6, Day 21; or until study drug discontinuation due to either disease progression or unacceptable toxicity; or other reasons whichever occurs first, as listed in Section 3.9. Each cycle of treatment is defined as 21 days of once daily osimertinib treatment. The Follow-up Phase will begin once a patient discontinues study drug or on completion of Treatment Phase, and will continue until 28 days after last dose, death, loss to follow up, consent withdrawal for study participation, or study end, whichever occurs first (see Section 3.9, 3.10, 3.11).

Osimertinib will be provided free of cost by the sponsor to clinical trial patient in the Treatment Phase. The sponsor shall provide the laboratory investigations for safety evaluation including hematology, biochemistry and ECG as mentioned in the Time and Event Schedule to monitor the safety throughout the study period.

Figure 1. Schematic Overview of the Study

SCREENING PHASE (VISIT 0)

Patients, or their legally acceptable representative, will provide written informed consent before any trial-specific procedures are performed. During the Screening Phase, eligibility criteria will be reviewed and a complete clinical evaluation will be performed as specified in the Time and Event Schedule. Screening procedures will be performed within 7 days before Cycle 1, Day 1. All baseline disease characteristics will be captured based evaluation performed as a part of routine clinical practice. The Screening laboratory tests, if any, must be completed within 7 days before Cycle 1, Day 1.

TREATMENT PHASE

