The Treatment Phase will extend from Cycle 1, Day 1 to Cycle 6, Day 21; or until study drug discontinuation due to either disease progression or unacceptable toxicity; or other reasons whichever occurs first, as listed in Section 3.9. Details of the procedures performed during the Treatment Phase are outlined in the Time and Events Schedules. Patients will be closely monitored for adverse events and other safety evaluations including laboratory investigations, concomitant medications. If disease progression is diagnosed before Cycle 6, Day 21, then the patient will discontinue study drug with completion of the End-of-Treatment Visits on the day of progression, and will enter the Follow-up Phase.

END-OF-TREATMENT VISIT (EOT)

An End-of-Treatment Visit is to be scheduled on Cycle 6, Day 21 of the study drug administration. In a case where patient discontinues the study treatment for any reason listed in Section 3.9 before Cycle 6, Day 21, last visit of the patient will be considered as End-of-treatment visit. Every effort should be made to conduct the telephonic End-of-Study Visit before the patient starts subsequent treatment.

FOLLOW UP PHASE (END-OF-STUDY)

A telephonic follow-up will be conducted 28 days after the EOT Visit. This will be considered as End-of-study visit.

The observation period including the Enrolment Visit and telephonic end-of-study visit will be up to a maximum duration of approximately 23 weeks for each patient.

5. Study Assessments

The investigator ensures the accuracy, completeness, and timeliness of the data recorded and of the provision of answers to data queries according to the Clinical Study Agreement.

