Appendix A to the Clinical Study Protocol.

6.3 Recording of adverse events

6.3.1 Time period for collection of adverse events

Adverse Events will be collected from patient actually taking the study drug throughout the entire treatment period and during the follow-up period until the end of the study. SAEs will be collected from the time at which informed consent is obtained until the end of the study.

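### Protocol Section 3.8 gives abstinence its own end date, 14 days short of the 6-week contraception rule in the same bullet

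*Protocol*

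**What the plan says.** The first bullet of Protocol Section 3.8 opens with the general rule: "Females of child-bearing potential should use reliable methods of contraception from the time of screening until 6 weeks after discontinuing study treatment". A list of acceptable methods follows. Total sexual abstinence comes first, and it is the only method in the list with a stated duration: "abstinence must be for the total duration of the trial and the follow-up period".

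The end of follow-up is set elsewhere. Protocol Section 4 says that the Follow-up Phase "will continue until 28 days after last dose", or ends sooner on death, loss to follow-up, withdrawal of consent or study end. SAP Section 5.2 repeats this. Section 4 also fixes the closing contact: "A telephonic follow-up will be conducted 28 days after the EOT Visit". It gives the whole observation period as "up to a maximum duration of approximately 23 weeks for each patient". Section 6.3.1 uses the term follow-up period for adverse event collection, which continues "during the follow-up period until the end of the study".

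Sections 6.6 and 6.6.1 set the pregnancy reporting window at 6 weeks after the last dose.

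**The concern.** One bullet gives two end dates for the same obligation. The general rule runs to day 42 after stopping drug, while the duration attached to abstinence runs only to the end of follow-up. The general rule is worded as *should* and the abstinence duration as *must*, so a site reader could take the parenthesis as the specific, binding instruction for that method.

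What is at stake is reproductive safety counselling. A woman relying on abstinence could be told that it may stop when follow-up closes, although the rule still has days to run. Table 1 schedules no contact after the end-of-study call, so no planned visit would correct the advice. The statistical analysis is not involved.

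**Working it through.** **Inputs**

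- Contraception rule for women: 6 weeks = 6 × 7 = 42 days after stopping treatment (Protocol 3.8).
- End of the Follow-up Phase: at most 28 days after the last dose (Protocol 4; SAP 5.2).
- Screening: up to 7 days (Protocol 4).
- Treatment: 6 cycles × 21 days = 126 days (Protocol 4).
- End-of-study call: 28 days after the end-of-treatment (EOT) visit (Protocol 4).
- EOT visit after premature discontinuation: "as soon as possible but not later than 7 days after discontinuation of study drug" (Protocol 3.9.1).
- EOT study day printed in Table 1: 131.

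**Step 1. Reproduce the plan's own figure.** Maximum observation = screening + treatment + follow-up = 7 + 126 + 28 = 161 days, and 161 / 7 = 23.0 weeks. This matches the stated maximum. A 42-day follow-up would give 7 + 126 + 42 = 175 days = 25.0 weeks, which does not match. The study's follow-up is therefore 28 days.

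**Step 2. Shortfall counted from the last dose.** 42 − 28 = 14 days; 14 / 42 = 33% of the required post-treatment window.

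**Step 3. Shortfall if follow-up is taken to end at the end-of-study call.**

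| EOT visit relative to last dose | Call, days after last dose | Shortfall |
|---|---|---|
| Same day | 0 + 28 = 28 | 42 − 28 = 14 days (33%) |
| Day 131 as in Table 1, last dose Day 126 | 131 + 28 − 126 = 33 | 42 − 33 = 9 days (21%) |
| 7 days later, the latest allowed by 3.9.1 | 7 + 28 = 35 | 42 − 35 = 7 days (17%) |

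The abstinence duration is below 42 days in every row. The shortfall exceeds 14 days if follow-up ends early through withdrawal or study end.

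**Step 4. Which figure is intended.** The 6-week figure in 3.8 agrees with the 6-week pregnancy reporting window in 6.6 and 6.6.1. The rules for men also agree with each other: 4 months of contraception in 3.8 and 4 months of follow-up of conceptions in 6.6.2. The abstinence parenthesis is the one element that does not fit.

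**The case against.** The strongest reply is that nothing conflicts. The opening sentence governs every method in the list, abstinence included, and a woman who abstains to day 42 satisfies both statements. On this view the parenthesis only says that abstinence must be continuous to count as a method, much as the vasectomy entry asks for confirmation of azoospermia. It does not call itself a minimum or a stopping date. This stands in part: no one is excused from the 6-week rule, and the 14 days are not days without a contraception requirement. The bullet still attaches to one method a duration shorter than the rule.

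A second reply is that follow-up period in 3.8 is not the defined term Follow-up Phase and could mean the 6-week window itself. The documents do not support that. Section 6.3.1 uses follow-up period for the study's own follow-up, and no section defines a longer one.

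Third, the 7-to-14-day range is not a strict bound. Section 4 also says that after early discontinuation the patient's last visit counts as the EOT visit. That visit could precede the last dose, which would bring the call before day 28. In addition, patients who continue osimertinib from commercial supply after the treatment phase have not stopped the drug, so the day counts describe only those who stop. Both points are correct. Neither changes the 14 days, which rest on the Follow-up Phase definition.

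Finally, the harm requires staff to rely on the parenthesis and overlook the sentence before it, and the consent form, which is not available here, may state the 6 weeks. That keeps the point minor.

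**Conclusion.** The concern holds as a small internal inconsistency. The duration stated for abstinence ends at least 14 days before the 6-week rule in the same bullet when counted from the last dose (33% of the window). If the end-of-study call is used instead, the shortfall is about 7 to 14 days, with the caveat on EOT timing given above.

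The conclusion assumes that follow-up period in 3.8 means the study's follow-up as defined in Section 4, and that the patient stops osimertinib at the end of study treatment. The number of women of child-bearing potential is not given, so the number affected cannot be estimated. Pregnancy reporting is unaffected, as are all endpoints, analysis sets and summaries. The correction is worth making but minor.

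**What to change.** In the first bullet of Protocol Section 3.8, replace the duration in the abstinence parenthesis so that abstinence must run "from the time of screening until 6 weeks after discontinuing study treatment", as in the opening sentence. Sections 6.6 and 6.6.1 need no change because they already use 6 weeks.

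The cost is one phrase in a protocol amendment. For a patient with the full 7-day screening who completes treatment, the stated abstinence period becomes 175 days (25.0 weeks) instead of 161 days (23.0 weeks). This only restates what the rule already requires, and it adds no visit, data collection or analysis.

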3.9 Discontinuation from study treatment

If a subject's study treatment must be discontinued, this will not result in automatic withdrawal of the subject from the study. If a subject discontinues study treatment for any reason before the end of the treatment phase, end-of-treatment assessments should be obtained and scheduled follow-up phase assessments should continued as specified in the Time and Events Schedule.

Patients may be discontinued from the study drug treatment in the following situations:

- The subject experiences disease progression (as per participating physician's assessment)
- Adverse Event (including laboratory abnormality or intercurrent illness) which, in the opinion of the investigator, indicates that continued participation in the study is not in the best interest of the patient
- The subject (or the subject's legally acceptable representative) withdraws consent for administration of study drug
- The subject received concurrent (non-protocol) anti-cancer treatment for NSCLC
- ILD/Pneumonitis
- Corneal ulcerations
- QTc interval prolongation with signs/symptoms of serious arrhythmia
- Pregnancy
- Any adverse event deemed to be related to osimertinib that requires a dose hold of more than 21 days will result in permanent discontinuation of osimertinib.
- Grade 3 or higher adverse reaction that does not improve to Grade 0-2 after withholding for up to 3 weeks

The primary reason for discontinuation of study treatment is to be recorded in the eCRF.

3.9.1 Procedures for discontinuation of a patient from study drug

At any time, patients are free to discontinue study drug or withdraw from the study (i.e., study drug and assessments), without prejudice to further treatment. A patient that decides to discontinue study drug will always be asked about the reason(s) and the presence of any adverse events. If possible, they will be seen and assessed by an Investigator(s). Adverse events will be followed up (See Section 6) and all study drugs should be returned by the patient.

Enrolled patients who discontinue the study prematurely should immediately stop taking study drug and complete the procedures described for End of Treatment Visit, as soon as possible but not later than 7 days after discontinuation of study drug.

If a patient is withdrawn from study, see Section 3.9, 3.10, 3.11.

3.10 Criteria for withdrawal

3.10.1 Withdrawal of the informed consent

Patients are free to withdraw from the study at any time (study drug and assessments), without prejudice to further treatment.

Reasons for withdrawal from the study:

- Eligibility criteria not fulfilled
- Death
- Withdrawal of consent.
- Lost to follow up (unsuccessful contact with patient despite every effort made by investigator)

Patients who withdraw consent for further participation in the study will not receive any further study drug or further study observation. Note that the patient may be offered additional tests to withdraw safely.

A patient who withdraws consent will always be asked about the reason(s) and the presence of any adverse events (AE). The Investigator will follow up AEs outside of the clinical study. If a patient withdraws from participation in the study, then his/her enrolment code cannot be reused. Withdrawn patients will not be replaced.

Patients will be considered lost to follow-up only if no contact has been established by the time the study is completed, such that there is insufficient information to determine the patient's status at that time. Patients who refuse continuing participation in the study, including telephone contact, should be documented as "withdrawal of consent" rather than "lost to follow-up." Investigators should document attempts to re-establish contact with missing patients throughout the study period. If contact with a missing patient is re-established, the patient should not be considered lost to follow-up and any evaluations should resume according to the protocol.

3.11 Discontinuation of the study

The study may be stopped if, in the judgment of AstraZeneca, study patients are placed at undue risk because of clinically significant findings that:

• meet individual stopping criteria or are otherwise considered significant

- are assessed as causally related to study drug,
- are not considered to be consistent with continuation of the study

Regardless of the reason for termination, all data available for the patient at the time of discontinuation of follow-up must be recorded in the CRF. All reasons for discontinuation of treatment must be documented.

In terminating the study, the Sponsor will ensure that adequate consideration is given to the protection of the patients' interests.

4. Study Plan and Timing of Procedures

Study is planned to be conducted according to plan described in Table 1.

[figure not shown]
The decision of patients to participate in this study must not, in any way, impact upon the standard of care that they are receiving or any benefits to which they are otherwise entitled. Prior to data collection, all patients must sign an informed consent form (ICF) allowing data collection and source data verification in accordance with local requirements and sponsor policy.

Patients with metastatic EGFR T790M mutation-positive NSCLC, who are eligible to osimertinib treatment as per locally approved prescribing information and ratified by an independent clinical judgment of treating physician will be evaluated for the inclusion into the current phase-IV study based on eligibility criteria. EGFR T790M positivity on plasma or tissue biopsy on PCR-based platform will be considered appropriate test. EGFR T790M must be performed after progressive disease on last line of therapy (on or after EGFR TKI therapy). In order to enrol approximately 60 patients, it is expected that approximately 70 patients will be screened.

Patient participation will include a Screening/Enrolment Phase, a Treatment Phase, and a Follow-up Phase. The Screening Phase will be up to 7 days prior to Cycle 1, Day 1. The Treatment Phase will extend from Cycle 1, Day 1 to Cycle 6, Day 21; or until study drug discontinuation due to either disease progression or unacceptable toxicity; or other reasons whichever occurs first, as listed in Section 3.9. Each cycle of treatment is defined as 21 days of once daily osimertinib treatment. The Follow-up Phase will begin once a patient discontinues study drug or on completion of Treatment Phase, and will continue until 28 days after last dose, death, loss to follow up, consent withdrawal for study participation, or study end, whichever occurs first (see Section 3.9, 3.10, 3.11).

Osimertinib will be provided free of cost by the sponsor to clinical trial patient in the Treatment Phase. The sponsor shall provide the laboratory investigations for safety evaluation including hematology, biochemistry and ECG as mentioned in the Time and Event Schedule to monitor the safety throughout the study period.

Figure 1. Schematic Overview of the Study

SCREENING PHASE (VISIT 0)

Patients, or their legally acceptable representative, will provide written informed consent before any trial-specific procedures are performed. During the Screening Phase, eligibility criteria will be reviewed and a complete clinical evaluation will be performed as specified in the Time and Event Schedule. Screening procedures will be performed within 7 days before Cycle 1, Day 1. All baseline disease characteristics will be captured based evaluation performed as a part of routine clinical practice. The Screening laboratory tests, if any, must be completed within 7 days before Cycle 1, Day 1.

TREATMENT PHASE

The Treatment Phase will extend from Cycle 1, Day 1 to Cycle 6, Day 21; or until study drug discontinuation due to either disease progression or unacceptable toxicity; or other reasons whichever occurs first, as listed in Section 3.9. Details of the procedures performed during the Treatment Phase are outlined in the Time and Events Schedules. Patients will be closely monitored for adverse events and other safety evaluations including laboratory investigations, concomitant medications. If disease progression is diagnosed before Cycle 6, Day 21, then the patient will discontinue study drug with completion of the End-of-Treatment Visits on the day of progression, and will enter the Follow-up Phase.

END-OF-TREATMENT VISIT (EOT)

An End-of-Treatment Visit is to be scheduled on Cycle 6, Day 21 of the study drug administration. In a case where patient discontinues the study treatment for any reason listed in Section 3.9 before Cycle 6, Day 21, last visit of the patient will be considered as End-of-treatment visit. Every effort should be made to conduct the telephonic End-of-Study Visit before the patient starts subsequent treatment.

FOLLOW UP PHASE (END-OF-STUDY)

A telephonic follow-up will be conducted 28 days after the EOT Visit. This will be considered as End-of-study visit.

The observation period including the Enrolment Visit and telephonic end-of-study visit will be up to a maximum duration of approximately 23 weeks for each patient.

5. Study Assessments

The investigator ensures the accuracy, completeness, and timeliness of the data recorded and of the provision of answers to data queries according to the Clinical Study Agreement.

